11.2 Secondary Objectives Analysis

Secondary efficacy objectives are not associated with any hypothesis testing.

All secondary efficacy objectives will be evaluated based on the Efficacy FAS, but analysis for the key secondary objective will be also repeated based on Efficacy PPS.

Similar to the primary efficacy objectives, a Cox PH model will be used to estimate absolute vaccine efficacy VE for each secondary objective.

11.3 Exploratory Objectives Analysis

All exploratory efficacy objectives will be evaluated based on the Efficacy FAS.

The measures for exploring efficacy are as follows:

- Number of deaths as derived from SAE forms
- Number of subjects with pneumonia as derived from AE forms
- Number of subjects with physician-confirmed otitis media as derived from AE forms

These will be evaluated by frequency tables both for QIVc and the non-influenza comparator.

The model used to estimate the exploratory efficacy objectives is similar to the model used for primary efficacy objectives, being related to the onset of the first occurrence of culture-confirmed influenza, due to any influenza H3N2 virus strains antigenically matched to the influenza H3N2 A / Singapore / GP2050 / 2015 (cell seed) strain.

12. IMMUNOGENICITY ANALYSIS

12.1 Blood Samples

The frequencies and percentages of subjects with blood draws will be summarized overall and by vaccine group, age group and “previously vaccination” status. Data will be tabulated for the FAS and PPS.

12.2 Primary Objectives Analysis

Not Applicable.

12.3 Secondary Objectives Analysis

Both Adjusted (see section 8.1) and Unadjusted estimates for GMTs, GMRs and pertaining two-sided 95% CIs will be calculated assuming log-normal distribution of the titers and will be completed by providing minimum, maximum and median titers for each vaccine group.

For the immunogenicity analysis, the measures for immunogenicity as determined by serum HI antibody titers for Day 1 (all subjects in immunogenicity subset), Day 22 (all “previously vaccinated” subjects receiving a single vaccine dose) or Days 29 and 50 (all “not previously vaccinated” subjects receiving 2 doses) for all four influenza strains are as follows:

- Geometric mean HI titer (GMT) on Day 1, Day 22 and Day 50 achieved by “previously vaccination” status of subjects.
- Percentage of subjects achieving seroconversion (defined as $HI \geq 1:40$ for subjects negative at baseline [$HI < 1:10$]; or a minimum 4-fold increase in HI titer for subjects positive at baseline [$HI \geq 1:10$]) after last vaccination (i.e. on Day 50 for subjects “not previously vaccinated” and on Day 22 for subjects “previously vaccinated”).
- Ratio of Geometric Mean HI titer (GMR) in subjects “not previously vaccinated” after Day 29 and Day 50 respectively relative to pre-vaccination.
- Ratio of Geometric Mean HI titer (GMR) in subjects “previously vaccinated” after Day 22 relative to pre-vaccination.
- Percentage of subjects “not previously vaccinated” with HI titer $\geq 1:40$ on Day 29 and Day 50

- Percentage of subjects “previously vaccinated” with HI titer $\geq 1:40$ on Day 22

Log-normal distributed data

All statistical analyses for HI will be performed on the logarithmically (base 10) transformed values. Results will be transformed back afterwards including the two-sided 95% confidence interval.

Individual HI titers below detection limit will be set to half that limit.

For each strain and each vaccine group, both unadjusted and adjusted estimates for GMTs, GMRs and pertaining two-sided 95% CIs will be calculated assuming log-normal distribution of the titers and will be completed by providing minimum, maximum and median titers for each vaccine group.

Log-transformed antibodies at Day 1, Day 22, and Day 50 for not previously vaccinated subjects and Day 1 and Day 22 for not previously vaccinated subjects will be modeled using ANCOVA with a factor for vaccination group, baseline-titer, country, and previous influenza vaccination. Adjusted Geometric means and adjusted geometric mean ratios and pertaining two-sided 95% confidence intervals will be calculated based on these models.

Analysis of binary data

Proportions of subjects with HI titers $\geq 1:40$ will be summarized at all time-points.

Percentages of Subjects with Seroconversion: The number and proportion of subjects achieving seroconversion in HI titers from pre-immunization at all-time points at which blood samples were drawn will be summarized.

All secondary endpoints for binary data will be tabulated for each of the influenza vaccine strains and for each of the vaccine groups, including the associated two-sided 95% confidence intervals according to Clopper-Pearson ([Clopper and Pearson 1934](#)).

Secondary immunogenicity objectives will be evaluated based on the FAS (immunogenicity). If the percentage of vaccinated subject excluded from the FAS (immunogenicity) is greater than 5%, a secondary analysis based on the PPS will be performed to complement the FAS.

12.4 Exploratory Objectives Analysis

In case of additional immunogenicity analyses, such as MN, the immune response will generally be characterized in a similar manner as described in Secondary Immunogenicity Endpoints:

- MN Geometric mean titers (GMTs) on Day 1 (all subjects), Day 22 (all “previously vaccinated” subjects receiving a single vaccine dose) or Days 29 and 50 (all “not previously vaccinated” subjects receiving 2 doses) for all 4 influenza strains.
- MN Geometric Mean Ratio (GMR) of Day 22/Day 1 (all “previously vaccinated” subjects receiving a single vaccine dose) or Day 29/Day 1 and Day 50/Day 1 (all “not previously vaccinated” subjects receiving 2 doses) for all 4 influenza strains.
- Percentage of subjects with at least a 4-fold rise in MN titer on Day 22 (all “previously vaccinated” subjects receiving a single vaccine dose) or Day 29 and Day 50 (all “not previously vaccinated” subjects receiving 2 doses) for all 4 influenza strains.

13. SAFETY ANALYSIS

The analysis of safety in this study will include summaries of the following categories of safety data collected for each subject:

- Vaccine exposure
- Solicited local and systemic adverse events
- Unsolicited adverse events
- Height and weight assessments

13.1 Analysis of Extent of Exposure

The overall time the subjects are under observation will be summarized by vaccine and overall and for naïve and non-naïve subjects and by age using summary statistics (mean, standard deviation, minimum, median, maximum) and compared between treatment arms.

13.1.1 Safety Completeness Analysis

Solicited adverse events

The safety completeness analysis on solicited adverse events aims to identify subjects who completed subject diary cards, irrespective of severity. The analysis will show the number of subjects with valid data by solicited adverse event and time point. Valid data in the context of the safety completeness analysis are all data entered in the subject diary card (including implausible values) except “Not done/unknown”.

Three summaries will be produced:

1. The frequencies of subjects who provide subject diary cards by vaccine group and collection method.
2. For each type of solicited adverse event (local, systemic) [and indicators of solicited adverse events, such as use of analgesic use] the frequencies of subjects *with valid data* by vaccine group, aggregated over time points and intervals: 30 min and 6 h – Day 7.
3. For each solicited adverse event, the frequencies of subjects *with valid data* by vaccine group aggregated over time points and intervals: 30 min and 6 h – Day 7.

For the corresponding percentages, the denominator will be the respective numbers of exposed subjects, i.e., subjects who received a vaccination, irrespective of whether a

subject diary card was present or not. All analyses will be based on the Safety Set (i.e. ‘as treated’).

13.2 Solicited Local and Systemic Adverse Events

The following adverse events are included in the subject diary card check list. Each adverse event will be assessed using a grading system.

Subjects < 6 years of age

Solicited local adverse events:

- Injection site induration
- Injection site erythema
- Injection site ecchymosis
- Injection site tenderness

Solicited systemic adverse events:

- Change of eating habits
- Sleepiness
- Vomiting
- Diarrhea
- Irritability
- Shivering
- Fever is also solicited but this is based on actual recorded body temperatures rather than subjective interpretation of fever by the subject

Subjects ≥6 years of age

Solicited local adverse events:

- Injection site induration
- Injection site erythema
- Injection site ecchymosis
- Injection site pain

Solicited systemic adverse events:

- Shivering
- Nausea
- Generalized myalgia

- Generalized arthralgia
- Headache
- Fatigue
- Vomiting
- Diarrhea
- Loss of appetite
- Fever is also solicited but this is based on actual recorded body temperatures rather than subjective interpretation of fever by the subject

Other solicited adverse events:

- Use of analgesics / antipyretics for prophylaxis
Use of analgesics / antipyretics for treatment
- Body temperature described in degrees Celsius or degrees Fahrenheit and summarized by route of body measurement

For erythema, ecchymosis, and induration recorded originally as diameters (mm), the following categorization(s) will be used to summarize the data for subjects < 6 years of age:

- 1-9 mm
- 10-25 mm
- 26-50 mm
- >50 mm
- Any: ≥ 1 mm

and for subjects ≥ 6 years:

- 1-24 mm
- 25-50 mm
- 51-100 mm
- >100 mm
- Any: ≥ 1 mm

Grading for pre-selected local and systemic adverse events are presented in Table 13.2-1.

Table 13.2-1: Grading of Solicited Local Adverse Events for All Subjects

	Reaction	Grade 0/None	Grade 1/Mild	Grade 2/Moderate	Grade 3/Severe
Local	Injection Site Tenderness/Pain	None	No interference with daily activity	Interferes with daily activity	Prevents daily activity
	Temperature	< 38.0°C	≥ 38.0 - 38.9°C	≥ 39.0 - 39.9°C	≥ 40.0°C
Systemic	Change of Eating Habits/ Loss of Appetite	None	Eating less than normal for 1 - 2 feeds/meals	Missed 1 or 2 feeds/meals	Missed more than 2 feeds/ meals
	Sleepiness	None	Shows an increased drowsiness	Sleeps through feeds/meals	Sleeps most of the time and it is hard to arouse him/her
	Vomiting	None	1-2 times in 24 hours	3 – 5 times in 24 hours	6 or more times in 24 hours or requires intravenous hydration
	Diarrhea	Fewer than 2 loose stools in 24 hours	2 - 3 loose stools in 24 hours	4 - 5 loose stools in 24 hours	6 or more loose stools in 24 hours or requires intravenous hydration
	Irritability	None	Requires more cuddling and is less playful than usual	More difficult to settle	Unable to console
	Shivering	None	Requires more cuddling and is less playful than usual	More difficult to settle	Unable to console
	Nausea	None	No interference with daily activity	Interferes with daily activity	Prevents daily activity
	Generalized Myalgia	None	No interference with daily activity	Interferes with daily activity	Prevents daily activity
	Generalized Arthralgia	None	No interference with daily activity	Interferes with daily activity	Prevents daily activity
	Headache	None	No interference with daily activity	Interferes with daily activity	Prevents daily activity
	Fatigue	None	No interference with daily activity	Interferes with daily activity	Prevents daily activity
	Fever	Captured as No (<38°C) or Yes (≥38°C)			

Other	Use of analgesics / antipyretics for treatment.	Captured as No or Yes
	Use of analgesics / antipyretics for prophylaxis.	Captured as No or Yes

Solicited adverse events will be reported at 30 minutes, at 6 hours on Day 1 and then daily until Day 7 using structured diaries. The analyses of solicited adverse events will be done based on the intervals: 30min and 6h – Day 7. In addition, solicited adverse events ongoing after Day 7 will be presented as unsolicited AE.

Body temperature will be summarized separately according to the 3 schemes described below and will be broken down by route of measurement according to the recommendations of the Brighton collaboration.

- by 0.5 °C increments from 36.0°C up to $\geq 40^\circ\text{C}$: <36.0 , ≥ 36.0 – <36.5 , ≥ 36.5 – <37.0 , ≥ 37.0 – <37.5 , ≥ 37.5 – <38.0 , ≥ 38.0 – <38.5 , ≥ 38.5 – <39.0 , ≥ 39.0 – <39.5 , ≥ 39.5 – <40.0 , $\geq 40.0^\circ\text{C}$.
- by 1.0 °C increments from 36.0°C up to $\geq 40^\circ\text{C}$: <36.0 , ≥ 36.0 – <37.0 , ≥ 37.0 – <38.0 , ≥ 38.0 – <39.0 , ≥ 39.0 – <40 , $\geq 40^\circ\text{C}$.
- <38.0 , ≥ 38.0 °C.

Fever (defined as a body temperature of $\geq 38^\circ\text{C}$ irrespective of route of measurement) will be integrated to the summaries as an indicator of a systemic adverse event.

Injection site pain and systemic AEs (except fever) occurring for the 7 days including each vaccination will be summarized according to “mild”, “moderate” or “severe”.

Each solicited local and systemic AE will also be further summarized as “none” versus “any”.

The analyses will encompass summaries of the data on five levels:

1. Daily reports of subjects with solicited adverse events.
2. Time of first onset of solicited adverse events (excluding 30 min measurement).
3. Solicited adverse events, maximum event severity by event on Day 1-7 without 30 min.
4. Duration of solicited adverse events.

5. Solicited adverse events and indicators of solicited adverse events, occurrence of at least one event by category (local, systemic) and interval Day 1-7 without 30 min.

For each of the time points or time intervals presented in the summaries, only subjects with at least one plausible observation (i.e., any non-missing values but excluding “Not done/unknown” and implausible values) for the solicited adverse events in the interval of interest will be considered. Subjects without plausible data (i.e. missing values or reported as “Not done/unknown” and implausible values) will be removed from the denominator to prevent a downward bias (towards zero).

Level 1: Daily reports of solicited adverse event

For each of the time points only subjects with at least one plausible observation (i.e., any non-missing values but excluding “Not done/unknown” and implausible values) for the solicited adverse event in the interval of interest will be considered. Subjects without plausible data (i.e. missing values or reported as “Not done/unknown” and implausible values) will be removed from the denominator in order to prevent a downward bias (towards zero). Data collected will be summarized (frequencies and percentages of subjects) by vaccine group, solicited adverse event, vaccination number and time point.

Level 2: Time of first onset of solicited adverse events

The time of first onset is defined, for each subject, for each solicited adverse event, as the time point on which the respective solicited adverse event first occurred. For erythema, ecchymosis and induration two thresholds will be used: ≥ 1 mm and ≥ 25 mm for children older than 6 years or ≥ 1 mm and ≥ 9 mm for children aged 6 and below.

Table 13.2-2: Example for Time to First Onset of Solicited Adverse Events

Vaccination	Subject Number	Day 1 ^a	Day 2	Day 3	Day 4	...	Day 7
1	001	None	Severe	Moderate	None	...	None
	002	Mild	None	None	Moderate	...	Missing
	003	Moderate	Mild	None	Severe	...	Mild
	004	Mild	Mild	None	None	...	None
2	001	None	None	None	None	...	Not done
	002	None	Mild	Mild	Missing	...	Missing
	003	Severe	None	Mild	Missing	...	None
	004	Missing	Missing	Missing	Severe	...	Mild

^a Exclude 30 minutes after vaccination.

For each vaccination the first onset of the adverse event will be used for each subject. For any vaccination the worst adverse event across all vaccinations per time point will be used. Note, ‘not done’ is treated identical to ‘missing’. A mock-up table is shown in Table 13.2-3 below.

Table 13.2-3: Time to First Onset of Solicited Adverse Events

Vaccine group A

Vaccination	Adverse event	Number (%) of Subjects						
		DAY 1 ^a (N=4)	DAY 2 (N=4)	DAY 3 (N=4)	DAY 4 (N=4)	...	DAY 7 (N=4)	
1	XY	n	4	4	4	4	...	3
		ANY	3 (75.0%)	1 (25.0%)	0 (0%)	0 (0%)	...	0 (0%)
		Mild	2 (50.0%)	0 (0%)	0 (0%)	0 (0%)	...	0 (0%)
		Moderate	1 (25.0%)	0 (0%)	0 (0%)	0 (0%)	...	0 (0%)
		Severe	0 (0%)	1 (25.0%)	0 (0%)	0 (0%)	...	0 (0%)
2	XY	n	3	3	3	2	...	2
		ANY	1 (33.3%)	1 (33.3%)	0 (0%)	1 (50.0%)	...	0 (0%)
		Mild	0 (0%)	1 (33.3%)	0 (0%)	0 (0%)	...	0 (0%)
		Moderate	0 (0%)	0 (0%)	0 (0%)	0 (0%)	...	0 (0%)
		Severe	1 (33.3%)	0 (0%)	0 (0%)	1 (50.0%)	...	0 (0%)
ANY	XY	n	4	4	4	4	...	3
		ANY	3 (75.0%)	1 (25.0%)	0 (0%)	0 (0%)	...	0 (0%)
		Mild	2 (50.0%)	0 (0%)	0 (0%)	0 (0%)	...	0 (0%)
		Moderate	0 (0%)	0 (0%)	0 (0%)	0 (0%)	...	0 (0%)
		Severe	1 (25.0%)	1 (25.0%)	0 (0%)	0 (0%)	...	0 (0%)

N: no. of subjects with data at a time point across all vaccinations.

n: no. of subjects with data at a time point for that specific vaccination.

^a Exclude 30 minutes after vaccination.

Level 3: Solicited adverse events, maximum event severity by event and interval

The **maximum event severity** will be defined if there is at least one plausible non-missing observation (excluding “Not done/unknown” and implausible values) within this time interval, Each subject’s data will be aggregated across the time points of the interval and summarized according to the maximal severity observed for each adverse event, followed by a summary across subjects for each vaccine. Subjects without any solicited

adverse events in the interval, i.e., missing values at each of the requested time points, will be removed from the denominator.

Level 4: Number of days with solicited adverse events

The number of days with the adverse event is defined irrespective of severity. This means at least ‘mild’ solicited adverse event that are assessed qualitatively. For erythema, ecchymosis and induration two thresholds will be used: ≥ 1 mm and ≥ 25 mm for children older than 6 years or ≥ 1 mm and ≥ 9 mm for children aged 6 years and below. If a solicited adverse event continues beyond Day 7, the period after Day 7 is added as an unsolicited adverse event.

The frequency distribution of the number of days will be provided in a summary table by vaccine and by adverse event.

Level 5: Solicited adverse events, occurrence of at least one event by category (local, systemic) and interval.

The **occurrence of at least one solicited adverse event** is defined as “any” for a subject if he/she reports greater than “none” for the respective event and “none” otherwise. For erythema, ecchymosis and induration two thresholds will be used for an event: ≥ 1 mm and ≥ 25 mm for children older than 6 years or ≥ 1 mm and ≥ 9 mm for children aged 6 years and below. The occurrence of at least one solicited adverse event (i.e., none versus any) will be summarized by category (i.e., local, systemic, any), by vaccine group, by vaccination (after each vaccination and after any vaccination) and by time interval.

Medications to treat or prevent pain or fever will be summarized by frequencies and percentages of subjects reporting use of the medications by interval 30 min, Day 1 – 7 (excluding 30 minutes after vaccination).

For details please refer to [section 7.1.1 of the protocol](#).

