7.1.1 Solicited Adverse Events

The term “reactogenicity” refers to selected signs and symptoms (“reactions”) occurring in the hours and days following a vaccination, to be collected by the subject for seven (7) consecutive days, using a pre-defined checklist in a diary card (i.e., solicited adverse events).

The following adverse events are included in the diary card check list. Each adverse event will be assessed using the grading system reported in the SAP.

Subjects < 6 years of age

Solicited local adverse events:

- Injection site induration
- Injection site erythema
- Injection site ecchymosis
- Injection site tenderness

Solicited systemic adverse events:

- Change of eating habits
- Sleepiness
- Vomiting
- Diarrhea
- Irritability
- Shivering
- Fever is also solicited but this is based on actual recorded body temperatures rather than subjective interpretation of fever by the subject.

Subjects ≥ 6 years of age

Solicited local adverse events:

- Injection site induration
- Injection site erythema
- Injection site ecchymosis
- Injection site pain

Solicited systemic adverse events:

- Shivering
- Nausea

- Generalized myalgia
- Generalized arthralgia
- Headache
- Fatigue
- Vomiting
- Diarrhea
- Loss of appetite
- Fever is also solicited but this is based on actual recorded body temperatures rather than subjective interpretation of fever by the subject.

Other solicited adverse events:

- Use of analgesics / antipyretics for prophylaxis.
- Use of analgesics / antipyretics for treatment
- Body temperature described in degrees Celsius or degrees Fahrenheit and summarized by route of body measurement.

The study staff must review the diary card with the subject and/or parent(s)/legal guardian(s) at the following visit (see sections 3.4.2, 5.2 and 5.3.1) and must directly record the solicited local and systemic adverse events on the appropriate Local and Systemic Adverse events eCRF. As described in Section 3.4.2, all solicited local and systemic adverse events that are legible must be recorded verbatim in the eCRFs, even if the values do not appear to be plausible.

If a solicited local or systemic adverse event continues beyond day 7 after vaccination, it will also be recorded as an AE on the AEs eCRF.

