7.1.3 Evaluation of Adverse Events

Every effort should be made by the investigator to evaluate safety information reported by a subject for an underlying diagnosis and to capture this diagnosis as the event in the AE page. In other words, the practice of reporting only symptoms (e.g., "cough" or "ear pain") are better reported according to the underlying cause (e.g., "asthma exacerbation" or "otitis media").

The severity of events reported on the Adverse Events CRF will be determined by the investigator as:

Mild: transient with no limitation in normal daily activity.
Moderate: some limitation in normal daily activity.
Severe: unable to perform normal daily activity.

The relationship of the study treatment to an AE will be determined by the investigator based on the following definitions:

1. Not Related

The AE is not related to an investigational vaccine if there is evidence that clearly indicates an alternative explanation. If the subject has not received the vaccine, the timing of the exposure to the vaccine and the onset of the AE are not reasonably related in time, or other facts, evidence or arguments exist that reasonably suggest an alternative explanation, then the AE is not related.

2. Possibly Related

The administration of the investigational vaccine and AE are considered reasonably related in time and the AE could be explained by exposure to the investigational vaccine or by other causes.

3. Probably Related

Exposure to the investigational vaccine and AE are reasonably related in time and no alternative explanation has been identified.

The relationship of the study treatment to an unsolicited AE will be determined by the investigator.

Note: solicited AEs will not be evaluated for relationship to study treatment. Each adverse event will be assessed using the grading system reported in the SAP.

Adverse events will also be evaluated by the investigator for the co-existence of any of the other following conditions:

- “Medically attended adverse event”: an adverse event that leads to a visit to a healthcare provider.
- “New onset of chronic disease” (NOCD): an adverse event that represents a new diagnosis of a chronic medical condition that was not present or suspected in a subject prior to study enrolment.
- AEs leading to withdrawal: adverse events leading to study or vaccine withdrawal.

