8.4.3.1.2 Analysis of Solicited Local, Systemic and Other Adverse Events

The solicited local and systemic adverse events for each age group is described in [Section 7.1.1](#).

All solicited adverse events will be summarized according to defined severity grading scales.

Frequencies and percentages of subjects experiencing each adverse event will be presented for each symptom severity. Summary tables showing the occurrence of any local or systemic adverse event overall and at each time point will also be presented.

Post-vaccination solicited adverse events reported from day 1 to Day 7 will be summarized for the intervals Day 1-3, Day 4-7, Day 1-7 by maximal severity and by vaccine group, excluding the 30 minute measurement, which will be summarized separately (and similarly for Day 29 to Day 35 solicited adverse events, for “not previously vaccinated” subjects). Injection-site erythema, ecchymosis and induration will be summarized according to categories based on linear measurements, please refer to the SAP for definition of categories.

Injection site pain and systemic adverse events (except fever) occurring up to 7 days after each vaccination will be summarized according to “mild”, “moderate” or “severe” categorization. For the definition of severity grades please refer to the [Section 7.1.3](#) of the protocol.

Each solicited local and systemic adverse event will also be further summarized as “none” versus “any”. “Any” will include reactions with a diameter of at least 1 mm.

Implausible measurements (for further definition see SAP) will be left out of the analysis.

Use of antipyretics and analgesics will be summarized by frequency and percentage of subjects reporting use. Summaries by type of use (prophylactic versus treatment) and by treatment arm will be provided.

Body temperature will be summarized by 0.5°C and 1.0°C increments from 36.0°C up to $\geq 40^\circ\text{C}$ and will be broken down by route of measurement and by age cohort (≥ 2 to < 9 years of age and ≥ 9 to < 18 years of age). In addition, fever will be summarized according to “mild”, “moderate” or “severe” categorization. For the definition of severity grades please refer to the SAP.

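### SAP Table 13.2-1 grades shivering with the irritability descriptors at all ages, so the planned severity tables for shivering at 6 to <18 years cannot be interpreted as written

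*SAP*

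**What the plan says.** SAP section 13.2 lists the diary-card events for two age groups. Shivering is on both lists and is the first systemic event under "Subjects ≥6 years of age". Irritability is on the under-6 list only. Protocol section 7.1.1 gives the same lists.

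Table 13.2-1 then gives one set of grades with no age split; its title is "Grading of Solicited Local Adverse Events for All Subjects". Shivering is mild when the child "Requires more cuddling and is less playful than usual", moderate when "More difficult to settle" and severe when "Unable to console". The irritability row directly above has the same three entries.

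On which scale governs, Protocol 7.1.1 says: "Each adverse event will be assessed using the grading system reported in the SAP". Section 7.1.3 repeats this after its note on solicited events. Protocol 8.4.3.1.2 points elsewhere. Its sentence on the three severity levels, which begins "Injection site pain and systemic adverse events (except fever) occurring up to 7 days after each vaccination will be summarized according to", is followed by a referral to Protocol 7.1.3 for the grade definitions. That section holds a daily-activity scale whose moderate grade is "some limitation in normal daily activity".

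**The concern.** Cuddling, playfulness and consolability describe a fretful young child. They say nothing about how strongly a subject shivers, and they do not fit a subject of up to 17 years. The identical wording of adjacent rows suggests a copying slip.

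Severity of shivering is a planned reactogenicity output under the secondary safety objective. If the grades have no meaning for older subjects, the reported numbers with mild, moderate or severe shivering have none either. A programmer who follows Table 13.2-1 and one who follows the cross-reference in Protocol 8.4.3.1.2 would also define moderate shivering differently.

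**Working it through.** The plan states no figure to reproduce. The check is a comparison of passages, followed by one piece of arithmetic on size.

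**Step 1. Rows side by side (SAP 13.2 event lists and Table 13.2-1).**

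| Event | Solicited <6 y | Solicited ≥6 y | What the grades describe |
|---|---|---|---|
| Irritability | yes | no | cuddling / settling / consoling |
| Shivering | yes | yes | cuddling / settling / consoling (identical text) |
| Nausea, myalgia, arthralgia, headache, fatigue | no | yes | interference with daily activity |
| Vomiting, diarrhea | yes | yes | counts in 24 hours |
| Change of eating habits / loss of appetite | yes | yes (as loss of appetite) | meals reduced or missed |

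For the older group, shivering is the only event whose grades belong to another event. Elsewhere section 13.2 does split by age where it matters: the size bands for erythema, ecchymosis and induration differ below and above 6 years.

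**Step 2. Which scale governs.** Protocol 7.1.1 and 7.1.3 both send solicited-event grading to the SAP. The daily-activity scale in 7.1.3 is introduced as the investigator's grading of events on the Adverse Events CRF, whereas solicited events go on a separate Local and Systemic eCRF (7.1.1). Table 13.2-1 is therefore the only shivering scale that the documents state for subjects ≥6 years. The cross-reference in 8.4.3.1.2 does not agree with this chain, but the disagreement is not specific to shivering: the SAP scales for vomiting, diarrhea, sleepiness and appetite also differ from 7.1.3.

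**Step 3. Which outputs use the grades.** SAP 13.2 plans mild/moderate/severe summaries of systemic events, first onset by severity (mock-up Table 13.2-3) and maximum severity (Level 3). Three outputs do not need the split between grades: none versus any, the number of days with the event (defined irrespective of severity), and the occurrence of at least one event (Level 5).

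**Step 4. Planned share of subjects in the age range.** Inputs from SAP Table 3-1: total 7,692, of whom 3,604 are ≥9 to <18 years.

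- Floor, counting only those ≥9 years: 3,604 / 7,692 = 46.9%. The protocol's table gives 3,606, also 46.9%.
- The documents do not give the number aged 6 to <9. The younger cohort is 7,692 − 3,604 = 4,088. If a fraction f of it is aged 6 to <9, the share is (3,604 + 4,088f) / 7,692.
- Even spread over seven years of age (assumption), f = 3/7: (3,604 + 1,752) / 7,692 = 5,356 / 7,692 = 69.6%, about 70%.
- A majority needs 7,692/2 − 3,604 = 242 subjects, so f = 242 / 4,088 = 5.9%.

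**The case against.** The strongest reply is that severity is captured on the diary cards. There are two versions, ≥2 to <6 and ≥6 to <18 years (Protocol 5.2.1), and Protocol 3.1 describes the solicited events on them as age appropriate. Their grade wording is not in the documents. If the older card offers suitable grades, the SAP row is a transcription slip and the data are sound. This stands as a limit on the claim: the documents do not show that shivering was collected on the wrong scale. It does not rescue the row, because in that case the SAP misdescribes what was collected.

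It is also fair that the consequence is small. Safety analyses are descriptive with no success criterion, both arms use the same scale under observer blinding, and SAP 8.5 presents ≥2 to <6, ≥6 to <9 and ≥9 to <18 years separately.

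A reader might infer more than the text supports:

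- *That the SAP contradicts the protocol's grading.* Protocol 7.1.1 and 7.1.3 delegate to the SAP, and the 7.1.3 scale is worded for a different form. What remains is one conflicting cross-reference, which affects several events.
- *That shivering alone is not comparable with the other systemic events.* Step 1 shows that no common scale was intended; counts, meals and daily activity sit side by side.
- *That every subject ≥6 years is affected.* Only those who report shivering receive a grade from 1 to 3. The percentages in Step 4 are the planned population in the age range, not the number of graded events.
- *That an infant scale was used.* The youngest subjects are 2 years old.

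**Conclusion.** The point holds as a wrongly stated rule in the SAP. For subjects 6 to <18 years, the only stated shivering grades are the irritability descriptors, and the severity tables built on them cannot be interpreted as written. The age range covers at least 46.9% of planned subjects; the figure of about 70% rests on an even spread of ages 2 to <9, which the documents do not give.

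None-versus-any summaries are largely unaffected. The qualification is that 'any' means a report above none, and if the older card carried the cuddling wording, a shivering adolescent who needs no comforting would fit no grade above none. Whether the collected data are impaired depends on that card. The effect is confined to one descriptive secondary safety item and does not touch any efficacy result, the sample size or alpha. The priority is low, but the correction is cheap and worth making before the tables are produced.

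**What to change.** 1. Retrieve the grade wording for shivering from both diary-card versions.
2. Split the shivering row of Table 13.2-1 by age group (<6 and ≥6 years) and make the ≥6-year grades match the ≥6 to <18 card. If that card offers daily-activity grades, use those already in the table for nausea, headache and fatigue.
3. If the card carried the cuddling wording, a new SAP row cannot regrade entries already collected. Report shivering at ≥6 years as none versus any only, or footnote its severity tables. This may already apply: SAP 8.5 describes the seed viruses of Seasons 1 to 3 in the past tense.
4. Reconcile the cross-reference in Protocol 8.4.3.1.2 (to 7.1.3) with Protocol 7.1.1 and 7.1.3 (to the SAP), so that one scale governs solicited systemic events. The table title, which says local although the table covers systemic events, can be corrected at the same time.

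The cost is one table row, one cross-reference and possibly the loss of one descriptive severity breakdown.
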